2.6 Analysis of the key secondary objective

2.6.1 Key secondary endpoints

The following are key secondary efficacy endpoints:

- Time-adjusted percent change in LDL-C from baseline after Day 90 and up to Day 330 (Year 1), defined as the average of percent changes from baseline to day 150, 270, and 330.
- Absolute change in LDL-C from baseline to Day 330 (Year 1)
- Percent change in Apo B from baseline to Day 330 (Year 1)
- Percent change in Lp(a) from baseline to Day 330 (Year 1)
- Percent change in non-HDL-C from baseline to Day 330 (Year 1)
- Percent change in total cholesterol from baseline to Day 330 (Year 1)

Secondary estimands corresponding to key secondary efficacy endpoints are defined similarly to the primary estimand. These endpoints, and the corresponding summary measures, are listed

Novartis	For business use only	Page 26
SAP amendment 4		CKJX839C12301

below. Population, treatment of interest, endpoints, and intercurrent events are defined similarly as for the primary estimand.

- Endpoint: time-adjusted percent change in LDL-C from baseline after Day 90 and up to Day 330 (Year 1). Summary measure: difference between treatment groups in mean time-adjusted percent change in LDL-C from baseline after Day 90 and up to Day 330 (Year 1).
- Endpoint: absolute change in LDL-C from baseline to Day 330 (Year 1). Summary measure: difference between treatment groups in mean absolute change in LDL-C from baseline to Day 330 (Year 1).
- Endpoint: percent change in Apo B from baseline to Day 330 (Year 1). Summary measure: difference between treatment groups in mean percent change in Apo B from baseline to Day 330 (Year 1).
- Endpoint: percent change in Lp(a) from baseline to Day 330 (Year 1). Summary measure: difference between treatment groups in mean percent change in Lp(a) from baseline to Day 330 (Year 1).
- Endpoint: percent change in non-HDL-C from baseline to Day 330 (Year 1). Summary measure: difference between treatment groups in mean percent change in non-HDL-C from baseline to Day 330 (Year 1).
- Endpoint: percent change in total cholesterol from baseline to Day 330 (Year 1). Summary measure: difference between treatment groups in mean percent change in total cholesterol from baseline to Day 330 (Year 1).

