2.6.2 Statistical hypothesis, model, and method of analysis

The key secondary endpoints will be analyzed using the same ANCOVA with multiple imputation using wash-out model as mentioned for primary endpoint except the time-adjusted percent change in LDL-C from baseline after Day 90 and up to Day 330. In the model baseline LDL-C will be replaced by baseline of respective endpoint. The estimate and corresponding 2-sided 95% confidence intervals of mean difference between treatment groups will be calculated. P-value for hypothesis test for mean difference will also be provided.

The time-adjusted percent change in LDL-C from baseline after Day 90 and up to Day 330 will be estimated using MMRM model. MMRM analysis (using control-based pattern mixture model for missing value imputation) will be performed on the percentage change in LDL-C from baseline over visits (Day 150, 270, 330) as specified for primary endpoint on each of the 100 imputed dataset. Then, linear combinations of the estimated means from visits Day 150, 270 and 330 will be used to compare treatment effects in terms of time-adjusted percent change in LDL-C. Treatment effects from these 100 MMRM analyses will then be combined using Rubin's Method. The estimate and corresponding 2-sided 95% confidence intervals of mean difference between treatment groups will be calculated. P-value for hypothesis test for mean difference will also be provided.

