2.6.3 Multiplicity adjustment

A hierarchical testing strategy will be applied to control the family-wise type I error rate at the one-sided significance level of alpha=0.025 to assess superiority of inclisiran over placebo.

Novartis	For business use only	Page 27
SAP amendment 4		CKJX839C12301

Hypotheses associated with the key secondary endpoints will be tested in the order listed above in Section 2.6.1.

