2.6.5 Supplementary analyses

Supplementary analyses of key secondary endpoints will be performed in subgroups as specified in Section 2.2.1. The MMRM model (using control-based pattern mixture model for missing value imputation) will be used to evaluate the difference between inclisiran and placebo groups in each subgroup.

Another supplementary analysis for Lp(a) will be applied in log-transformed scale using same MMRM without multiple imputation specified above.

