5.7 Statistical models

5.7.1 Multiple Imputation Wash-out model

A multiple imputation washout model will be utilized for the primary efficacy analysis of the percentage change in LDL-C from baseline to Day 330 endpoint. The washout model can be thought of as a modified control-based PMM that will be used to explore the possibility of missing data being MNAR for subjects who discontinued the study early. For subjects who discontinued the study early, their missing values will be imputed under the assumption that their outcome would be similar to those in the placebo group with similar background characteristics. For subjects in the inclisiran group only missing Day 330 values will be imputed. For subjects in the placebo group their missing values over all visits after early termination will be used to account for uncertainty in the imputation process and results from the imputed datasets will be combined using Rubin's method. Further details are provided below.

For the placebo group the following variables will be included in a multiple imputation procedure (SAS PROC MI), this assumes missing data are MAR:

- Baseline value of efficacy measurement (continuous)
- Observed value of efficacy measurement at Day 90 (continuous)
- Observed value of efficacy measurement at Day 150 (continuous)
- Observed value of efficacy measurement at Day 270 (continuous)
- Observed value of efficacy measurement at Day 330 (continuous)
- Observed value of efficacy measurement at Day 360 (continuous)

For the subjects in the inclisiran group who completed first 3 doses and have data available after Day 330 (considered to have completed the Study Part 1) the following variables_will be included in a multiple imputation procedure (SAS PROC MI), this assumes missing data are MAR:

- Baseline value of efficacy measurement (continuous)
- Observed value of efficacy measurement at Day 330 from the inclisiran group (continuous)

For the remaining subjects in the inclisiran group the following variables will be included in a multiple imputation procedure (SAS PROC MI), this assumes missing data are MNAR:

• Baseline value of efficacy measurement (continuous)

Novartis	Confidential	Page 45 of 48
Clinical Study Report Appendix 16.1.9, v1.0		Study No. CKJX839C12301

Novartis	For business use only	Page 44
SAP amendment 4		CKJX839C12301

• Observed value of efficacy measurement at Day 330 from the placebo group (continuous)

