- 6. A total of 100 fully imputed datasets will be created (M=100). Since multiple imputation is a stochastic method, slight differences in output can be expected for different initial states of the random number generator. The seed numbers will be identified in the SAS programs to allow for reproducibility.
- 7. After the missing data imputation is completed using the above steps, absolute change/percentage change values will be calculated in each of the imputed datasets at each visit.
- 8. These 100 datasets will be analyzed using ANCOVA models with fixed effects of treatment group: baseline age group and baseline LDL-C as a covariate for the percent change of LDL-C from baseline to Day 330 primary efficacy endpoint. PROC MIXED with (repeated / group=treatment) statement which allows separate variance to estimate for treatment groups will be used.

Novartis	For business use only	Page 45
SAP amendment 4		CKJX839C12301

9. Treatment effects (difference in least squares (LS) means between treatments) from these 100 analyses will then be combined using Rubin's Method via SAS PROC MIANALYZE procedure for each endpoint.

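### The washout imputation handles Lp(a) on the raw scale with normal-theory steps, so imputed values can be negative, percent changes extreme, and power lost at the fourth key secondary endpoint

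*SAP*

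**What the plan says.** SAP 2.6.1 lists percent change in Lp(a) at Day 330 fourth of six key secondary endpoints, ahead of non-HDL-C and total cholesterol. SAP 2.6.3 states that "A hierarchical testing strategy will be applied to control the family-wise type I error rate at the one-sided significance level of alpha=0.025", and that "Hypotheses associated with the key secondary endpoints will be tested in the order listed above".

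SAP 2.6.2 says "The key secondary endpoints will be analyzed using the same ANCOVA with multiple imputation using wash-out model as mentioned for primary endpoint". Only time-adjusted LDL-C is excepted, and the one adaptation is to use each endpoint's own baseline as covariate.

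In SAP 5.7.1 the variables that are imputed are measured values. For inclisiran participants not counted as having completed Part 1, the list is the baseline value and "Observed value of efficacy measurement at Day 330 from the placebo group (continuous"). Steps 1 and 2 fill placebo gaps by MCMC and then by monotone regression. Step 3 uses PROC MI for inclisiran completers, and step 4 uses its MNAR statement for the remaining inclisiran participants. Step 7 then derives the changes: "absolute change/percentage change values will be calculated in each of the imputed datasets at each visit". By SAP 2.1.1 the divisor is the participant's own baseline. No transform, bound or predictive mean matching is stated.

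SAP 2.6.5 adds one log-scale analysis, for Lp(a) alone: "Another supplementary analysis for Lp(a) will be applied in log-transformed scale using same MMRM without multiple imputation".

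**The concern.** A normal regression on raw concentrations has one residual SD for everyone. If Lp(a) is right-skewed and varies in proportion to its level, the few participants with high values set that SD, and it is then added to participants whose baseline may be much smaller. Nothing keeps the draw above zero, and dividing by a small baseline magnifies it. The result is between-imputation variance that comes from the scale chosen for imputation and not from the data.

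No planned Lp(a) analysis would reveal this. The sensitivity analysis in SAP 2.6.4 uses the model of SAP 5.7.2, which also imputes measured values and derives percent change afterwards. The log-scale analysis contains no imputed values.

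At stake is the fixed testing order. A failure at Lp(a) caused by an inflated standard error would stop formal testing of the two endpoints behind it.

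**Working it through.** **Inputs from the documents.** 141 enrolled and 2:1 allocation (SAP 1.1), so 141 × 2/3 = 94 and 141 × 1/3 = 47. One-sided 0.025 (SAP 2.6.3). 100 imputations, unequal-variance ANCOVA and Rubin's rules (SAP 2.5.2, 5.7.1). The plan gives no figure for Lp(a) spread, within-person variation or missing data, so there is none to reproduce.

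**Assumptions.** Lognormal baseline with geometric SD g; within-person variation proportional to level, with coefficient of variation CV.

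**Step 1, the mechanism in closed form.** Take a placebo Day 330 value equal to baseline times noise. With s = ln g, the root mean square of baseline is median × exp(s²), so the common residual SD is CV × median × exp(s²). For g = 3 and CV = 20%: exp(1.0986²) = 3.34, and the SD is 0.20 × 3.34 = 0.67 medians. The baseline at quantile q is 3^z(q) medians.

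| Baseline quantile | Baseline (medians) | SD of imputed percent change | Chance of a negative draw |
|---|---|---|---|
| 10% | 0.245 | 0.669/0.245 = 273 points | Φ(-0.245/0.669) = 0.36 |
| 25% | 0.477 | 0.669/0.477 = 140 points | Φ(-0.477/0.669) = 0.24 |
| 50% | 1 | 67 points | Φ(-1/0.669) = 0.07 |

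On the log scale the SD is about 20 points at every level and a negative value is impossible. One imputed inclisiran value at the 10% quantile adds about 273/94 = 2.9 points to the between-imputation SD of the arm mean, against 20/94 = 0.2 on the log scale. The median cancels, so the unit of Lp(a) does not matter.

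**Step 2, simulation across assumptions.** 94 against 47, ANCOVA with the endpoint's own baseline and separate arm variances, true effect -15%, missing inclisiran values imputed from placebo, g = 2.5 to 3.5, CV = 15 to 25%:
- imputed values below zero: about 4 to 18%;
- power lost relative to log-scale imputation: about 0 to 14 points with 1 missing value, 2 to 45 points with 4;
- at g about 1.65: almost no loss.

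**Step 3, a separate simulation by missing-data rate.** N = 141, true effect -20%, log-SD 1.1 (g = 3.0), within-person log-SD 0.25, gaps imputed from baseline and age group. The 5% row used 100 imputations, the other rows 20.

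| Day 330 missing | Raw: SE, power | Log: SE, power |
|---|---|---|
| 1% | 4.6, 0.94 | 4.3, 0.995 |
| 5% | 8.4, 0.60 | 4.5, 0.99 |
| 10% | 11.9, 0.27 | 4.7, 0.99 |

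At 5% missing, 12% of imputed values were negative, and 32% among imputed participants in the lowest baseline quartile. With log-SD 0.5 (g = 1.65), 2.1% were negative and power was 0.995 raw against 1.00 log. With an LDL-C-like spread (log-SD 0.25), 0.1% were negative and the two SEs were equal at 3.5.

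**Step 4, no treatment effect.** In the same simulation (5% missing, 400 replicates) the one-sided rejection rate was 0.008 on the raw scale and 0.02 on the log scale, against the nominal 0.025.

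**The case against.** Several objections stand.
- **The skew is not in the documents.** They give no Lp(a) distribution. The log-scale analysis in SAP 2.6.5 suggests that the sponsor expected skew, but not how much.
- **Missing data may be few.** Injections are given by site staff (protocol 6.6.1), participants who stop treatment stay in follow-up (protocol 9.1.1), and an early-exit visit after Day 270 is mapped to Day 330 (SAP Table 2-1). These features limit the problem without removing it.
- **Absolute power is fragile.** When baseline also carries within-person noise, log-scale imputation itself passes in only about 64 to 99% of trials. The difference between the methods is more reliable than either level.
- **Normality is partly inferred.** Steps 1 and 2 name MCMC and monotone regression; steps 3 and 4 name no regression option.
- **The list does not fit Lp(a) literally.** It includes Days 90 and 270, when protocol 8.3.2 schedules no Lp(a) sample.

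Stronger readings are tempting, but the documents do not support them. A reader might infer that every participant with low Lp(a) gets a negative value; only those with an imputed value are exposed, and most draws stay positive. A reader might infer inflated type I error because the endpoint is alpha-controlled; step 4 shows the opposite direction. A reader might extend the point to the primary endpoint, which uses the same model; but entry requires LDL-C above 130 mg/dL (protocol 5.1), so baselines are well away from zero, whereas no criterion bounds Lp(a) from below. The endpoints ahead of Lp(a) in the order do not depend on its result.

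**Conclusion.** The concern holds as a matter of efficiency and plausibility of the imputed values. The SAP text supports the mechanism: raw-scale imputation, no bound, and division by own baseline afterwards. Its size rests on assumptions. With geometric SD 2.5 to 3.5, CV 15 to 25% and a true effect of -15%, the cost ranges from nothing to 14 points of power with one missing value, and from 2 to 45 points with four. It is negligible if skew is mild, and absent if no Lp(a) value needs imputing. The consequence is confined to Lp(a) and, through the testing order, to non-HDL-C and total cholesterol. The change is worth making because it is cheap and leaves the question being asked unchanged.

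**What to change.** In SAP 5.7.1, and in 5.7.2 for the Lp(a) sensitivity analysis, state that for Lp(a) the baseline and visit values are imputed on the natural-log scale and back-transformed before percent change is computed. The same sentence should name the visits at which Lp(a) is sampled. The ANCOVA, estimand and testing order stay as they are. Leave the supplementary log-scale MMRM without imputation as planned: its different missing-data assumption is useful in itself.

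The cost is one SAP sentence and one transform option in the program, with no change to data collection.

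Timing matters. Section 1 of the appendix that contains the SAP describes an analysis added after the Part 1 database lock, and protocol 6.4 has the trial team unblinded after that lock. If Part 1 is unblinded, do not replace the tested analysis. Report the number of imputed Lp(a) values at Day 330 and the share below zero, and add log-scale imputation as a labelled sensitivity analysis. If few or no values were imputed, those counts alone may settle the point.

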5.7.2 Control based Pattern-Mixture model

A control-based PMM will be used to explore the possibility of missing data being MNAR for subjects who discontinued the study. For subjects who discontinued the study without any further follow-up data, their missing values after study discontinuation will be imputed under the assumption that their outcome would be the similar to those in the placebo group with similar background characteristics. For subjects who did not discontinue the study, their intermittent missing values will be imputed based on the MAR assumption. Multiple imputation will be used to account for uncertainty in the imputation process and results from the imputed datasets will be combined using Rubin's method. Further details are provided below.

The covariates and baseline characteristics which can be predictive of the response will be included in a multiple imputation procedure (SAS PROC MI) and will include the following:

- Baseline value of efficacy measurement (continuous)
- Observed value of efficacy measurement at Day 90 (continuous)
- Observed value of efficacy measurement at Day 150 (continuous)
- Observed value of efficacy measurement at Day 270 (continuous)
- Observed value of efficacy measurement at Day 330 (continuous)
- Observed value of efficacy measurement at Day 360 (continuous)
- 1. Intermittent missing data will be imputed using MCMC methods, assuming MAR, within each treatment group. SAS PROC MI will be utilized for this step using the MCMC impute=monotone option. A total of 100 datasets will be created. These datasets will be utilized in Step #2.
- 2. The remaining missing values with a monotone missing data pattern will be imputed in this step. Control-based PMM imputation will be performed. With this imputation model, the missing efficacy measurements in the inclisiran group will not be constructed from the observed data in the inclisiran group but rather from the observed data in the placebo group. We will also use this model to impute missing efficacy measurements in the placebo group. The MNAR statement in SAS PROC MI will be used to impute missing values under the aforementioned assumptions. Baseline age group will be included in the imputation model. This will be performed for the 100 datasets. After this step, the 100 datasets will be fully imputed.
- 3. A total of 100 fully imputed datasets will be created (M=100). Since multiple imputation is a stochastic method, slight differences in output can be expected for different initial states of the random number generator. The seed numbers will be identified in the SAS programs to allow for reproducibility.

Novartis	For business use only	Page 46
SAP amendment 4		CKJX839C12301

- 4. After the missing data imputation is completed using the above steps, absolute change/percentage change values will be calculated in each of the imputed datasets at each visit.
- 5. These 100 datasets will be analyzed using the MMRM for the primary and key secondary efficacy endpoints.
- 6. Treatment effects (difference in LS means between treatments) from these 100 analyses will then be combined using Rubin's Method via SAS PROC MIANALYZE procedure for each endpoint.

Confidential	Page 48 of 48
Clinical Study Report Appendix 16.1.9, v1.0	
For business use only	Page 47
	Confidential 6.1.9, v1.0 For business use only

SAP amendment 4 CKJX839C12301

5.8 Rule of exclusion criteria of analysis sets

The protocol deviations (PD) and other criteria leading to complete exclusion from analyses sets may be included in this section and would be finalized before study DBL.
